## I. PURPOSE OF THE STUDY AND BACKGROUND

### A. Purpose of the Study

The proposed study “Integrated Community-Clinical Linkage Model to Manage Diabetes among South Asians” aims to test the effectiveness of a multi-level diabetes management intervention compared to usual care. The primary outcome is reduction in hemoglobin A1c (HbA1c) for patients with baseline HbA1c of  $>7\%$ . The secondary outcomes include enhanced use of community and social services and increased self-efficacy.

The integrated intervention involves:

1. An electronic health record (EHR) intervention for primary care providers (PCPs) utilizing embedded alerts to identify South Asian patients with uncontrolled diabetes.
2. Registry-driven community health worker (CHW)-led health coaching for patients. Using a stepped-wedge design, we will implement the study in 20 NYC PCP clinics enrolling 886 South Asian patients at- risk for Type 2 Diabetes Mellitus (T2DM).
3. Linkage to culturally relevant community-level resources
4. CHW-integration into primary care teams. The project will leverage Health Information Technology (HIT) tools to support integration of CHWs in healthcare teams, feedback between healthcare providers and CHWs, and establish a referral mechanism between CHWs, patients, and community resources

In addition, using a mixed-methods approach and the RE-AIM evaluation framework, we aim to systematically assess the implementation process and delineate factors that influence adoption, sustainability, and scalability of the integrated EHR-CHW intervention within applied practice settings.

This will be achieved through the completion of:

5. Provider Surveys (n=80) to capture data on satisfaction with workflow before and after intervention, information sources for EHR-CHW initiatives before and after intervention, acceptability of and satisfaction with the integrated EHR-CHW intervention, and barriers and facilitators of point-of-care use of the tools.
6. Key Informant Interviews (n=100) with physician champions at each clinic and/or administrator of each clinic, Healthfirst representatives, community advisory board members, research staff, and CHWs. At baseline, the interviews will be incorporated into the workflow analysis to assess current satisfaction and usage of EHR and health coaching. At follow-up, the interviews will assess barriers and facilitators to the implementation and adoption process of the integrated EHR-CHW intervention, fidelity to the interventions, and to solicit recommendations for the replication and scalability of the intervention to other clinics and insurer organizations.

**Impact:** This multi-level study will inform efforts to manage diabetes in a high-risk population and generate a reproducible and sustainable model for use in healthcare and community settings that engage vulnerable populations with a high burden of chronic disease. The contributions of this study to generalizable knowledge are further described in the “Background”.

## B. Background

**B1. South Asians are a rapidly growing population in the US and NYC.** Asian Americans currently compose 5% of the US population and approximately 32% of the immigrants entering the country. The US Census Bureau projects that by 2060 the number of Asian Americans nationally will grow to over 39 million, approximately 9.3% of the US population. In this proposal, we focus on the South Asian community (persons with ancestry from India, Bangladesh, Pakistan, or other parts of the South Asian continent). This community is among the largest and fastest growing Asian subgroups in the nation. In NYC, the South Asian community grew by 49% from 2000 to 2010 (216,179 to 323,675, respectively). Across South Asian groups, a significant portion of the community live in poverty (ranging from 17% of Asian Indians to 32% of Bangladeshis), have limited English proficiency (LEP) impacting access to care (ranging from 25% of Asian Indians to 53% of Bangladeshis), and have poor access to culturally appropriate community resources. For the purposes of our study, South Asians will be defined as individuals who self-identify as South Asian, including those from India, Bangladesh, Pakistan, Sri Lanka, Nepal, and Bhutan, Guyana, Trinidad.

**B2. South Asians in the US experience diabetes disparities.** Diabetes prevalence in the US South Asian community are high, with national data revealing the highest prevalence of diagnosed diabetes among Asian Indians compared to other Asian groups and compared to non-Hispanic whites. In NYC, population-based studies reveal strikingly high diabetes rates among South Asians. South Asians in NYC have significantly higher prevalence of clinically measured diabetes (35.4% vs 10.8%) and nearly five times the odds of having diabetes compared to whites (Adjusted Odds Ratio: 4.88, 95% CI [1.52, 15.66]). Additionally, the prevalence of self-reported diabetes diagnosis among South Asians of normal weight (using adjusted-BMI guidelines for Asians) in NYC is more than triple the rates of diabetes among non-Hispanic whites of normal weight (10.2% vs 2.9%, respectively). Thus, scalable and translatable interventions that promote diabetes management in this population may have significant potential for public health impact.

**B3. Asian Americans have lower rates of diabetes screening and poorer provider- and self-management of diabetes than other communities.** Nationally representative data indicates that Asian Americans are the least likely racial and ethnic group to receive recommended diabetes screening, with a 34% lower adjusted odds compared to non-Hispanic whites. In a population-based study in NYC, we have found that Asian Indians have lower average rates of diabetes management practices. Providers were significantly less likely to perform recommended guidelines for diabetes management, including foot checks or eye examinations. Interventions targeting health systems, primary care physicians, and patients are salient for improving diabetes management and outcomes in this community.

**B4. Team-based care and intensive diabetes self-management programs in clinical settings are effective in improving Hemoglobin A1c (HbA1c).** The US Preventive Services Taskforce has found sufficient evidence for three key strategies to improve diabetes management among patients including 1) Multi-disciplinary team-based care 2) Intensive lifestyle (diet or physical activity) interventions coupled with counseling, and 3) Identification and tracking of diabetic patients at risk through electronic health record (EHR)-based platforms according to risk and use

guidelines. Despite the evidence for these interventions, questions still remain as to the most effective members of the healthcare team to deliver lifestyle interventions, mechanisms for the coordination of care within healthcare settings, and the effectiveness of these strategies in LEP communities. Further, studies have found that social determinants of health, including low self-efficacy, low social support, food insecurity, and poor built environment are associated with higher levels of HbA1c (a key clinical marker for diabetes management), suggesting that clinically-oriented interventions should be coupled with interventions that address patients' social context.

**B5. Incorporating Community health workers (CHWs) into healthcare teams can improve diabetes related outcomes.** A substantial body of evidence demonstrates that CHWs are viewed as trusted sources of information and can be a natural bridge and effective strategy to disseminate efficacious interventions between underserved communities and the health care system. With the advent of the patient-centered medical home model, primary care practices (PCPs) increasingly aim to work in an integrated coordinated care manner for patients. A growing evidence base suggests that the addition of CHWs to the primary care team is a low-cost and cost-effective approach to improve care and adherence for patients with chronic disease. A recent review of the impact of CHWs on diabetes management found that on average, CHW interventions produce 0.2% reduction in HbA1c with the greatest reduction ( $>0.5\%$ ) among individuals at the most elevated levels. A 0.2% reduction in HbA1c is associated with 10% reduction in mortality, and 0.5% reductions in HbA1c considered clinically significant. In African American and Latino communities, studies that have integrated CHWs into clinical teams have demonstrated higher reductions in HbA1c. Our own work has demonstrated that a culturally adapted CHW-led intervention in community-based settings is acceptable and efficacious in improving HbA1c control, weight loss, self-efficacy and social support, and health behaviors for South Asian patients with diabetes. The integration of CHWs in clinical settings to support team-based diabetes management for patients, and reimbursement options for this workforce, offers a unique opportunity for sustainable, scalable models for diabetes management and linkage to community-based resources.

**B6. Health information technology (HIT) strategies and EHR data can be leveraged to improve diabetes management and link patients to community resources.** EHR data can identify candidates for recommended follow-up and targeted risk-reducing interventions and facilitate physician referral of patients to counseling and other services. The use of clinical decision support systems (CDSS) or alerts can increase provider adherence to screening and monitoring guidelines for diabetes management and prevention, such as foot and retinal exams, as well as cholesterol & hemoglobin A1c testing. EHR-based goal-setting modules, intention exercises, and tailored reminders to encourage behavior change during clinical encounters has enhanced provider capacity to counsel patients. Recent efforts to use EHR systems and HIT strategies to identify, refer and link patients to community resources, including social services, have found it to be feasible, acceptable and effective. For example, an EHR-based e-prescribing model that linked patients to community resources according to patient needs generated 253,479 personalized prescriptions for more than 113,000 participants. Nearly 83% of the recipients found the referral very useful, and 19% of them adhered to the referral. To date, such models have not been widely implemented in small primary care settings that serve high-risk immigrant communities. Furthermore, referral systems may be limited in their ability to appropriately connect to culturally appropriate services for linguistically isolated, LEP, and minority populations.

**B7. The effect of integrated, multi-level interventions to improve diabetes management has not been well-tested.** Recent studies have demonstrated that EHR access and communication between the PCP and the CHW can facilitate the acceptance and effectiveness of emerging care

management models and lead to improved patient outcomes, yet no one has conducted studies in small primary care settings. Several studies have noted that the integration of health systems and provider, patients, and community level components may enhance the impact of diabetes management interventions. However, few studies have examined the impact of integrating multi-component interventions and how best to engage both physician and non-physician members of the healthcare team, including CHWs, in these efforts. Scalable and sustainable models that assess the implementation process of integrating multi-level intervention in clinical practice settings are needed, particularly for immigrant and LEP populations like the South Asian community. Our study will meet this need and aligns with the proposed Center of Excellence (COE) thematic focus on addressing scientific knowledge gaps of the health interventions that work across Asian American subgroups in community and clinical contexts.

## Contributions

[figure not shown]
The goal of this study is to evaluate the effectiveness and integrated intervention to decrease HbA1c among South Asians four components: 1) an EHR-based registry function to increase with uncontrolled diabetes; 2) CHW-led health coaching of behavior change; 3) HIT-enabled and CHW-facilitated relevant community resources for patients; and 4) HIT-enabled other members of the healthcare team (See **Figure 1**).

This study is innovative in four main areas. First, though a integrated EHR-CHW approaches, our study would represent multi-level approach that combines EHR-based tools to identify CHW-led coaching, HIT-enabled community referrals, and diabetes management in a high risk community served by small provider practices, including primary care, are often the immigrant, and other underserved populations. Our study uniquely assesses both effectiveness outcomes and informs the replication of integrated models in other primary care settings and for other communities, aligning with the proposed COE's thematic focus. Second, our culturally adapted CHW-led diabetes management intervention has demonstrated efficacy, feasibility, and acceptability among South Asians in innovative in four main areas. Our study uniquely assesses both effectiveness outcomes and implementation processes. Thus, it informs the replication of integrated models in other primary care settings and for other communities, aligning with the proposed COE's thematic focus.

Second, our culturally adapted CHW-led diabetes management intervention has demonstrated efficacy, feasibility, and acceptability among South Asians in community settings, and the proposed study can be reproduced for integration into clinical settings.

Third, our study offers a replicable model for linking patients within clinical systems to culturally relevant community settings and resources that can impact social support and other material conditions which have a demonstrable effect on diabetes outcomes. CHWs will play a linkage role

Figure 1: Multi-Level Diabetes Management

implementation process of a multi-level, with uncontrolled diabetes, including identification of South Asian patients registered patients to promote health identification and referral to culturally care coordination between the CHW and

limited number of studies have the first to examine integration of a high risk patients, culturally adapted CHW-physician feedback to improve primary care practice settings. Small provider of care for minority, and implementation processes. Thus, it informs the replication of integrated models in other primary care settings and for other communities, aligning with the proposed COE's thematic focus. Second, our culturally adapted CHW-led diabetes management intervention has demonstrated efficacy, feasibility, and acceptability among South Asians in innovative in four main areas. Our study uniquely assesses both effectiveness outcomes and implementation processes. Thus, it informs the replication of integrated models in other primary care settings and for other communities, aligning with the proposed COE's thematic focus.

that is facilitated by health IT tools, thus expanding their reach, efficiency, and effectiveness. Finally, through a multi-sector partnership that represent community, healthcare, payers, and health information technology, *the study will disseminate tools, products, and processes to inform scalable community-clinical linkage models.*

### C. Study Design

#### C1. Overall Design/Clinic Selection/Clinic Enrollment

We will use a randomized controlled trial design with staggered-entry and a waitlisted control group to compare the effectiveness of an alert and registry-driven CHW-led coaching compared with usual care among patients with HbA1c at  $>7\%$ . Randomization will be at the individual-level and stratified by PCP, meaning eligible treatment and control participants will be randomized for each PCP. PCPs will be clustered into waves, aligning with the original stepped-wedge design. Entry into the study will be staggered in three waves, with each wave consisting of six to seven PCPs (See Figure 1). All 20 PCPs will be recruited and enrolled by month 6 of Year 1 (study period 6, Figure 1), and we will assign 6-7 practices into each of the 3 waves upon enrollment. For each PCP, there will be a total of two rounds of consecutive six-month CHW intervention periods for the treatment group: 1 month for recruitment and enrollment of treatment participants and five months of community health worker-led group education sessions (approximately one session per month). Data related to the study outcomes will be extracted from EHR systems a total four times (baseline, 6 month, 12 month, and 18 month) for each PCP; we will be comparing EHR data from 443 treatment participants with 443 control participants. Prior to allocation into treatment group, each treatment participant will be matched to a control participant based on age, gender, and BMI. Treatment participants will be split into two groups and assigned to either first or second round. All control participants will be waitlisted during the first round and will be offered the full CHW group education sessions during the second round as a point of service (i.e., not for research purposes).

Randomization at each PCP will occur during the first round. PCPs will be placed into waves based on geographic location and CHW caseload considerations. PCPs will be eligible for participation if they have a) an overall patient volume of  $N \geq 1000$  ; b) at least 70% of the patient population is South Asian; and c) the practice has used EHR for at least 12 months. All PCPs will sign a Memorandum of Understanding (MOU) between the PCP and NYU outlining study commitments.

There are four primary research groups for this study: 1) 446 treatment participants who will receive the CHW intervention; 2) 446 waitlisted control participants who may receive the CHW intervention as a point of service at a later point (de-identified EHR data collection only); 3) 40 subjects who will participate in provider surveys; and 4) 35 subjects who will participate in qualitative key informant interviews.

Figure 1. Recruitment, Enrollment, and CHW Intervention Timeline

Participant A�elar Projections	Year 1		Year 2		Year 3		Year 4		Year 5		Enrollment by wave 2022	Cumulative enrollment for entire study				
	Apr - June 2018	July - Sept 2018	Oct - Dec 2018	Jan - Mar 2019	Apr - June 2019	July - Sept 2019	Oct - Dec 2019	Jan - Mar 2020	Apr - June 2020	July - Sept 2020	Oct - Dec 2020	Jan - Mar 2021	Apr - June 2021	July - Sept 2021	Oct - Dec 2021	Jan - Mar 2022
Wave 1																
PCP1			Recruit/ Enroll N=44	CHW intervention		CHW intervention										
PCP2			Recruit/ Enroll N=44	CHW intervention		CHW intervention										
PCP3			Recruit/ Enroll N=44	CHW intervention		CHW intervention										
PCP4			Recruit/ Enroll N=44	CHW intervention		CHW intervention										
PCP5			Recruit/ Enroll N=44	CHW intervention		CHW intervention										
PCP6			Recruit/ Enroll N=44	CHW intervention		CHW intervention										
PCP7			Recruit/ Enroll N=44	CHW intervention		CHW intervention										
Wave 2																
PCP8					Recruit/ Enroll N=44	CHW intervention		CHW intervention								
PCP9					Recruit/ Enroll N=44	CHW intervention		CHW intervention								
PCP10					Recruit/ Enroll N=44	CHW intervention		CHW intervention								
PCP11					Recruit/ Enroll N=44	CHW intervention		CHW intervention								
PCP12					Recruit/ Enroll N=44	CHW intervention		CHW intervention								
PCP13					Recruit/ Enroll N=44	CHW intervention		CHW intervention								
Wave 3																
PCP14					Recruit/ Enroll N=44	CHW intervention		CHW intervention								
PCP15					Recruit/ Enroll N=44	CHW intervention		CHW intervention								
PCP16					Recruit/ Enroll N=44	CHW intervention		CHW intervention								
PCP17					Recruit/ Enroll N=44	CHW intervention		CHW intervention								
PCP18					Recruit/ Enroll N=44	CHW intervention		CHW intervention								
PCP19					Recruit/ Enroll N=44	CHW intervention		CHW intervention								
PCP20					Recruit/ Enroll N=44	CHW intervention		CHW intervention								

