## *2. Data collection and consenting with waitlisted control participants*

The NYU study team will only be collecting de-identified EHR data with control participants (n=443). EHR data will include clinical measures related to diabetes (e.g., HbA1c, BMI) and will be obtained from regularly generated diabetes registry lists that practices generate as part of quality improvement initiatives and these measures will be tracked over time. The PCPs will be conducting the de-identification and the link to the unique identifier will remain with the PCP staff. NYU study team members will not have access to these links. Beyond EHR data collection, no other data collection will occur with control participants (e.g., no survey data collection) and the control group will not have any interaction with study personnel for the purposes of research. PCPs will invite control participants to CHW education sessions at a later time (post round 1 of CHW intervention with treatment participants) as a point of service (i.e., not for research

purposes). The PCPs themselves are not involved in the research aside from providing NYU with de-identified EHR data.

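### Round-2 treated patients have no assured untreated concurrent control at their own PCP, the index visit is tied to no round, and the >80% power is not shown to apply to this schedule

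*Combined protocol and SAP*

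**What the plan says.** Section I.C1 sets the schedule for each PCP:

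- Timing of randomisation: "Randomization at each PCP will occur during the first round".
- Treatment arm: "Treatment participants will be split into two groups and assigned to either first or second round". Neither the method nor the proportion is given.
- Control arm: "All control participants will be waitlisted during the first round and will be offered the full CHW group education sessions during the second round". The list of research groups in the same section is softer: "waitlisted control participants who may receive the CHW intervention as a point of service at a later point". Section C2, under data collection with waitlisted controls, agrees on timing: "PCPs will invite control participants to CHW education sessions at a later time (post round 1 of CHW intervention with treatment participants". It also limits control data to de-identified EHR extracts, so no record of attendance is planned.
- Waves: "PCPs will be placed into waves based on geographic location and CHW caseload considerations".
- Intended contrast: "we will be comparing EHR data from 443 treatment participants with 443 control participants".

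Section III.B1 (Aim 1) defines response as an HbA1c fall of at least 0.5% within six months of an index visit. It fits a logistic mixed model with a clinic random effect, quarter effects and a treatment indicator indexed by person only. The Power Calculation claims more than 80% power for a 10-point difference with 886 patients, 15% loss and 20 PCPs. The Sampling paragraph describes about 22 patients per clinic per half-year for one year, and speaks of control quarters and treatment quarters. Figure 1, as extracted, shows "Recruit/ Enroll N=44" once per PCP.

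**The concern.** At any one PCP, the sessions are offered to every control in the same half-year in which the round-2 treated patients receive them. Those treated patients can be compared with controls from the preceding half-year, with controls at PCPs in other waves, or with controls who may themselves be attending. The first comparison is not concurrent. The second is not randomised, because waves are formed by geography and caseload. The third is diluted by an amount nobody will be able to measure.

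The model does not settle which is meant. Quarter effects adjust for calendar time but do not supply an untreated control at the same PCP. The treatment indicator cannot distinguish a treated patient before round 2 from the same patient after it, or a control before the offer from one after it. Because the index visit is not tied to a round, the plan as written allows round-2 treated patients to be scored against exposed controls, or before they have been treated. The choice could also be made after the outcomes have been seen. The primary estimand, the protection given by randomisation and the meaning of the power statement all depend on that missing definition.

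**Working it through.** **Inputs from the plan.** 443 per arm (I.C1); two-sided 0.05, 10-point difference, 15% loss, 20 PCPs (III.B1). After loss, 443 × 0.85 = 376 per arm.

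**Assumptions.** The control response rate is not stated, so I use 10% to 50%. The round split is not stated; an even split gives 376 / 2 = 188 treated in round 1.

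**Formula** (pooled z, no continuity correction, p̄ the weighted mean rate):

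power = Φ{ [ |p1 − p0| − 1.96 √(p̄(1−p̄)(1/n1 + 1/n0)) ] / √(p1(1−p1)/n1 + p0(1−p0)/n0) }

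**Step 1: the plan's own figure.** For 35% v 45% with 376 per arm: (0.10 − 1.96 × 0.03573) / 0.03554 = 0.84, so power is 80.0%. In reverse, 80% power needs 376 per arm and 376 / 0.85 = 442.4, rounded up to 443. The stated sample size therefore reproduces as a parallel-group calculation.

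**Step 2: round-1 treated v all controls.** This contrast is concurrent and within PCP. For 35% v 45% with 188 v 376: p̄ = 0.3833; (0.10 − 1.96 × 0.04343) / 0.04384 = 0.34, so power is 63%.

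**Step 3: everyone indexed in round 1.** Half the treatment arm is still untreated at six months, so the average difference is 10 × 0.5 = 5 points with 376 v 376. For 35% v 40%: (0.05 − 1.96 × 0.03531) / 0.03526 = −0.54, so power is 29%.

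| Control rate | 376 v 376, 10 points | 188 v 376, 10 points | 376 v 376, 5 points |
|---|---|---|---|
| 10% | 97% | 89% | 55% |
| 15% | 93% | 81% | 44% |
| 20% | 89% | 75% | 38% |
| 35% | 80% | 63% | 29% |
| 50% | 79% | 61% | 28% |

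The 188 v 376 contrast is below 80% for control rates from about 16% to 75%. With 40% of the arm in round 1 (150 v 376) it falls below 80% from about 12%; with 60% (226 v 376), from about 19%.

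**Step 4: both rounds pooled through the quarter effects.** I used a linear approximation of the planned model: waves of 7, 6 and 7 PCPs, half-year periods, an even split, all controls indexed in round 1, and a clinic correlation of 0 to 0.05. The variance of the treatment effect, relative to the full 376 v 376 contrast, depends on how waves overlap:

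- Waves starting half a year apart: 1.13 to 1.15.
- Waves 2 and 3 starting together, half a year after wave 1: 1.25 to 1.27.
- No overlap: 1.43 to 1.50. The upper value equals (1/188 + 1/376) / (2/376) = 1.5, so round-2 treated patients then add nothing to Step 2.

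Dividing 376 by the ratio gives power at control rates of 10%, 20% and 35% of 95%, 85% and 75% for 1.13, and 93%, 81% and 71% for 1.25. Figure 1 as extracted is too broken to say which overlap applies.

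**Step 5: enrolment totals.** 22 × 2 × 20 = 880, close to 886, so the Sampling figure counts both arms. It also agrees with 44 per PCP in Figure 1.

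**The case against.** The strongest reply has five parts.

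*The power claim is met on some readings.* This stands. At control rates of about 15% or less, even 188 v 376 keeps at least 81%, and pooling keeps more than 80% at 20% under favourable wave overlap. A reader might infer that no reading of the schedule reaches 80%, or that the trial is simply underpowered. The documents do not support either, because the control rate, split, uptake and overlap are not given.

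*A clean window already exists.* This is largely right. Controls are waitlisted through round 1 and the endpoint is at six months, so a control indexed at the start of round 1 has an untreated window. But the plan never says that this is the index, nor what the index is for round-2 treated patients.

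*Rounds may have been assigned at random.* A reader might infer biased assignment and put a false-positive rate on it. The method is unstated, which is not the same as non-random. Any such rate would need a selection shift that nothing in the documents supplies, so none is given here.

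*Enrolling twice does not contradict randomising once.* Agreed. Section I.C1 gives each round its own month to enrol treated patients. What remains is that the Sampling figure counts both arms per half-year and keeps wording from the stepped-wedge design.

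*Leaving out round-2 treated patients sits badly with intention to treat, and random rounds alone do not secure the contrast.* Both parts have force. Under C2 and VI.A, treated patients are invited, screened and consented after randomisation, with about 40% expected to be interested; under VI.G controls need no consent. The remedy has to address this.

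**Conclusion.** The concern holds. Round-2 treated patients have no assured untreated concurrent control at their own PCP; *assured* is the right strength, because controls are offered the sessions and need not attend. The index visit is undefined by round for both arms, and the treatment indicator cannot repair that. These two statements rest on the text alone.

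The power conclusion is conditional. More than 80% is a sound figure for a parallel trial with a control rate up to about 35%, and is missed only slightly above that. It has not been shown for the planned schedule. At 35%, the rate that reproduces 443 per arm, the readings examined give 29% (everyone indexed in round 1), 63% (round-1 treated only) and roughly 63% to 75% (pooled, relying on non-randomised comparisons across waves). All assume a 10-point effect, 15% loss and an even round split. The index definition must be settled before outcome data are examined.

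**What to change.** 1. Wherever round 1 has not started, assign treated patients to rounds at random within PCP. Elsewhere, report how rounds were assigned, and label the contrast non-randomised if the assignment was not random.
2. Define the index date by arm and round before outcome data are examined. Make the primary comparison round-1 treated patients v controls indexed at the start of round 1, using HbA1c dated before the controls' offer at that PCP. Analyse everyone randomised to round 1 whether or not they later consent, where de-identified EHR data allow. Otherwise state that the treated group is selected after randomisation.
3. Report the pooled comparison including round-2 treated patients, and the 12- and 18-month comparisons, as secondary.
4. Restate power for the chosen comparison as a table by control rate and round split.
5. Reconcile the half-yearly enrolment figure and the references to control and treatment quarters in the Sampling paragraph with round-1 randomisation in I.C1.

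The timing of the controls' offer is left to the investigators.

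**Cost.** Wording changes, a random round list for PCPs not yet started, and the month of the offer recorded per PCP. No patients or tests are added, since HbA1c is already extracted with month and year (III.A2). The price is lower stated power at most control rates, and round-2 treated patients leave the primary contrast.
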